4.2 Phase I

4.2.1 Dose Escalation

Phase I will consist of a radioactivity escalation part with the objective of determining the MTCA. For phase I, subjects enrolled will have unresectable, locally advanced or metastatic tumours expressing NTSR1 originating from either the pancreas (PDAC), colon and rectum (CRC), stomach (GC), gastrointestinal stromal tumours (GIST), head and neck region (SCCHN) or bone (ES).

The study screening period includes a screening administration of ¹⁷⁷Lu-3BP-227 to assess the tumour uptake of each subject by whole body scan (planar scintigraphy, 1 or 2 timepoint(s) at the investigator's discretion) and optional single photon emission computed tomography (SPECT)/CT scans (up to 2 at the investigator's discretion). Only subjects with a tumour uptake higher than nontumoural surrounding tissue (based on investigator's decision) will be deemed eligible for treatment. The screening period will last 3 weeks but can be extended by up to 2 weeks if this is required for logistical reasons. Subjects who participated in the imaging study, Study D-FR-01087-002, with ¹¹¹In-3BP-227 (also called ¹¹¹In-IPN01087) and who have an uptake of ¹¹¹In-3BP-227 in tumour lesions that is more avid than in the nontumoural surrounding tissue based on whole body imaging (planar scintigraphy), as judged by the investigator, can also be considered for enrolment in this study, provided that they fulfil all other inclusion criteria and do not meet any of the exclusion criteria and were imaged with ¹¹¹In-3BP-227 before the first treatment administration (therapeutic dose) of ¹⁷⁷Lu-3BP-227.

During the treatment phase, it is planned that each subject will receive ¹⁷⁷Lu-3BP-227 fractionated into two i.v. administrations separated by 4 to 5 weeks (+4 weeks in case of reversible AEs) (Figure 1). The safety evaluation will be done over 4 weeks between Cycle 1 and Cycle 2 and over 6 weeks between Cycle 2 and end of core trial (EOCT). During this period, subjects will have repeated imaging for the calculation of individual dosimetry data and will be monitored for signs of toxicity.

Tumour response will be assessed on CT or MRI, as well as with ¹⁸F-FDG-PET scans at the EOCT visit, (corresponding to 6 weeks after the second administration).

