- a the ED visit will take place within 14 days after ED from the study and at the latest 5 weeks after the last IMP administration, the visit will correspond to an EOCT visit. For subjects who received the screening IMP administration and found ineligible to participate to the study, an ED visit will be performed within 5 weeks (+ 2 weeks) after the IMP screening administration to assess the safety. At least, clinical laboratory tests (e.g. haematology and biochemistry), AEs and concomitant medication/therapy will be collected. If the subject is not able to come for an on-site visit, the visit may be performed by phone call. The clinical laboratory tests may be done locally.
- b follow-up visits will take place every 3 months (±2 weeks) and will start after the EOCT, ED or EOAC visit. Efficacy will be assessed until disease progression, administration of any other chemotherapy or radiotherapy, lost to follow-up, withdrawal of consent, death or a maximum of 2 years, whichever occurs first (see Section 6.2.3). After disease progression is confirmed, no further CT/MRI scans will be required for tumour/disease assessment. The survival status and safety of the subjects will continue to be monitored as indicated in Section 8.1.2.3 until lost to follow-up, withdrawal of consent, death or a maximum of 5 years, whichever occurs first.
- c the screening period can be extended by two weeks if this is required for logistical reasons.
- d Day 1 of Cycle 1 is the day of the first treatment administration. Day 1 of Cycle 2 and each potential subsequent cycle may coincide with Day 29 of the previous cycle if all safety assessments are performed and allow for the next administration.
- e in case of toxicity requiring a delay, the next treatment administration will be delayed by up to 4 weeks.
- f whole body ceCT or ceMRI including brain unless a similar exam has already been performed within 1 month prior to Day -21.
- g Cycle 1 Day 1 ¹⁸FDG-PET between Day -21 and Day 1.
- h screening administration will be done after confirmation of eligibility (i.e. after all other screening assessments have been performed), minimum 1 week before the first treatment administration.

Procedures and			CORE TRIAL [v]										EOCT	Long-term							
assessments	Screening		Treatment Period								or	Follow-up									
	Screening				Cycle 1					Cycle 2									ED [a]	[b]	
	D-21 to D-1	D1 [d]	D2	D3	D4	D5	D7	D 15	D 22	D29	D1 [d]	D2	D3	D4	D5	D7	D15	D22	D29	D43	

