4.4.3. Best overall response: all time points

The best overall response is determined once all the data for the patient is known.

Best response determination in trials where confirmation of complete or partial response IS NOT required: Best response in these trials is defined as the best response across all time points (for example, a patient who has SD at first assessment, PR at second assessment, and PD on last assessment has a best overall response of PR). When SD is believed to be best response, it must also meet the protocol specified minimum time from baseline. If the minimum time is not met when SD is otherwise the best time point response, the patient's best response depends on the subsequent assessments. For example, a patient who has SD at first assessment, PD at second and does not meet minimum duration for SD, will have a best response of PD. The same patient lost to follow-up after the first SD assessment would be considered inevaluable.

¹ A 'positive' FDG-PET scan lesion means one which is FDG avid with an uptake greater than twice that of the surrounding tissue on the attenuation corrected image.

Table 1 – Time point response: patients with target (+/-non-target) disease.

Target lesions	Non-target lesions	New lesions	Overall response
CR	CR	No	CR
CR	Non-CR/non-PD	No	PR
CR	Not evaluated	No	PR
PR	Non-PD or not all evaluated	No	PR
SD	Non-PD or not all evaluated	No	SD
Not all evaluated	Non-PD	No	NE
PD	Any	Yes or No	PD
Any	PD	Yes or No	PD
Any	Any	Yes	PD

CR = complete response, PR = partial response, SD = stable disease, PD = progressive disease, and NE = inevaluable.

Table 2 – Time point response: patients with non-target disease only.

Non-target lesions	New lesions	Overall response
CR	No	CR
Non-CR/non-PD	No	Non-CR/non-PDa
Not all evaluated	No	NE
Unequivocal PD	Yes or No	PD
Any	Yes	PD
CR = complete respon NE = inevaluable.	nse, PD = progressi	ve disease, and

a 'Non-CR/non-PD' is preferred over 'stable disease' for non-target disease since SD is increasingly used as endpoint for assessment of efficacy in some trials so to assign this category when no lesions can be measured is not advised.

Best response determination in trials where confirmation of complete or partial response IS required: Complete or partial responses may be claimed only if the criteria for each are met at a subsequent time point as specified in the protocol (generally 4 weeks later). In this circumstance, the best overall response can be interpreted as in Table 3.

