4.4.4. Special notes on response assessment

When nodal disease is included in the sum of target lesions and the nodes decrease to 'normal' size (<10 mm), they may still have a measurement reported on scans. This measurement should be recorded even though the nodes are normal in order not to overstate progression should it be based on increase in size of the nodes. As noted earlier, this means that patients with CR may not have a total sum of 'zero' on the case report form (CRF).

In trials where confirmation of response is required, repeated 'NE' time point assessments may complicate best response determination. The analysis plan for the trial must address how missing data/assessments will be addressed in determination of response and progression. For example, in most trials it is reasonable to consider a patient with time point responses of PR-NE-PR as a confirmed response.

Patients with a global deterioration of health status requiring discontinuation of treatment without objective evidence of disease progression at that time should be reported as 'symptomatic deterioration'. Every effort should be made to document objective progression even after discontinuation of treatment. Symptomatic deterioration is not a descriptor of an objective response: it is a reason for stopping study therapy. The objective response status of such patients is to be determined by evaluation of target and non-target disease as shown in Tables 1–3.

Conditions that define 'early progression, early death and inevaluability' are study specific and should be clearly described in each protocol (depending on treatment duration, treatment periodicity).

In some circumstances it may be difficult to distinguish residual disease from normal tissue. When the evaluation of complete response depends upon this determination, it is recommended that the residual lesion be investigated (fine

Overall response First time point	Overall response Subsequent time point	BEST overall response
CR	CR	CR
CR	PR	SD, PD or PR ^a
CR	SD	SD provided minimum criteria for SD duration met, otherwise, PD
CR	PD	SD provided minimum criteria for SD duration met, otherwise, PD
CR	NE	SD provided minimum criteria for SD duration met, otherwise NE
PR	CR	PR
PR	PR	PR
PR	SD	SD
PR	PD	SD provided minimum criteria for SD duration met, otherwise, PL
PR	NE	SD provided minimum criteria for SD duration met, otherwise NE
NE	NE	NE

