#### 1.3.2.2 Pharmacodynamic/efficacy assessments

- Tumour assessment according to Response Evaluation Criteria in Solid Tumors (RECIST) criteria v1.1 for target and non-target lesions assessed locally (by ceCT/MRI) at screening, at Day 1 of cycle 1 (removed from protocol V7.0), at EOCT/ED visit, at Day 29 of second and fourth additional cycles (if applicable), at EOAC/ED visit (if applicable) and every 3 months during long-term follow-up;
- Tumour assessment according to PERCIST criteria v1.0 for target and non-target lesions assessed locally at Day 1 of cycle 1, at EOCT/ED visit and at EOAC/ED visit (if applicable);
- Tumour markers in serum assessed at Day 1 of both cycles 1 and 2, at EOCT/ED visit, at Day 1 of each additional cycle (if applicable) and at EOAC/ED visit (if applicable) including Carcinoembryonic antigen (CEA) (all subjects), Cancer Antigen (CA) 19-9 (all subjects except SCCHN), CA72-4 (subjects with GC) (removed from protocol V7.0), Tissue Polypeptide antigen (TPA) (subjects with SCCHN) (removed from protocol V7.0) and serum Lactate Dehydrogenase (LDH) and Bone Specific Alkaline Phosphatase (BSAP) for ES;

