#### **3.2.18.1 Best Overall Response**

The BOR will be presented by treatment group at the end of the core trial, at the end of the additional cycles and at the end of the long-term follow-up.

BOR will be derived as the highest objective response achieved by the subject based on measurable lesions ((i.e. target, non-target and new lesions) from the time of first treatment until disease progression or the end of period and will be classified as: CR > PR > Non-CR/Non-PD (NCR/NPD) > SD > PD > NE.

If SD is believed to be the best response, it must also meet the minimum time from baseline of 56 days. If the minimum time is not met, the subject's best response will be based on the subsequent assessments.

According to RECIST guideline, any response CR or PR must be confirmed at least 4 weeks later, or as close to this timepoint as possible.

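### SAP 3.2.18.1 requires CR/PR confirmation at least 4 weeks later, but the core trial schedules one post-baseline scan, so its confirmed ORR can be 0% from scan timing alone

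*SAP*

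**What the plan says.** **Response rule.** SAP 3.2.18.1 presents BOR at three points: the end of the core trial, of the additional cycles and of long-term follow-up. BOR runs from first treatment "until disease progression or the end of period". Citing the RECIST guideline, the section adds that "any response CR or PR must be confirmed at least 4 weeks later, or as close to this timepoint as possible". Stable disease (SD) as best response needs at least 56 days from baseline. SAP 3.2.18.2 computes ORR from this BOR.

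**Scan schedule.** Protocol 4.2.1 states "Tumour response will be assessed on CT or MRI" and places that assessment at EOCT, six weeks after the second administration. After screening, the RECIST assessments in SAP 1.3.2.2 are "at EOCT/ED visit, at Day 29 of second and fourth additional cycles (if applicable"), then the end of additional cycles and long-term follow-up. In Protocol Attachment 1, Table 8, footnote b, "follow-up visits will take place every 3 months", within two weeks either way, starting after EOCT, early discontinuation or the end of additional cycles. Protocol 6.2.4 and 10.1.2 allow unscheduled scans but do not require them.

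**Attached RECIST (Protocol Attachment 4).** Where confirmation applies, section 4.4.3 says "Complete or partial responses may be claimed only if the criteria for each are met at a subsequent time point". Sections 4.4 and 4.6.1 require confirmation in non-randomised trials whose primary endpoint is response.

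**Endpoint status.** Protocol 4.4.1.1 makes the maximum tolerated (or administered) cumulative activity the Phase I primary endpoint. ORR is secondary, and its definition in Protocol 12.2.7 does not mention confirmation. The Synopsis does specify confirmed response for Phase II. SAP section 5 declares no change from the protocol.

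**The concern.** A confirmation rule needs two post-baseline scans at least 28 days apart. The core trial schedules one, and that scan marks the end of the period over which core-trial BOR is derived. Followed literally, the rule gives a result that reflects the calendar and not the treatment.

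This cut is used. SAP 3.2.24 makes the end of the core trial an interim analysis. Protocol 12.2.9 bases the clinical study report on data up to the last subject's EOCT and sends follow-up and additional-cycle data to an addendum. A reader of the main report could take a 0% ORR as evidence of inactivity.

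**Working it through.** **1. Where the core trial ends.** Protocol 4.5 gives a maximum of 21 weeks. The schedule windows reproduce it:
- screening 21 + 14 = 35 days
- Cycle 1, with the visit window and maximum delay, 28 + 7 + 28 = 63 days
- second administration to EOCT 42 + 7 = 49 days
- total 35 + 63 + 49 = 147 days = 21 weeks

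So the period ends at the EOCT visit.

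**2. When the scan falls.** Nominally the second administration is on day 29 and EOCT on day 29 + 42 = 71, which is 70 days after first dose. With all windows used it is 63 + 49 = 112 days after first dose. Early discontinuation uses the same assessments as EOCT. Table 8, footnote v gives any third cycle the Cycle 2 schedule, so it adds no scan before EOCT.

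**3. Time left for confirmation.** Days from the EOCT scan to the end of the period: 0. Days needed: 28. Responses confirmable on scheduled scans: none. A core-trial response could be confirmed only if an unscheduled scan showed it by 70 − 28 = 42 days after first dose and the EOCT scan then repeated it.

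**4. Effect on ORR**, with one partial response (PR) at EOCT and exact 95% intervals (the method in Protocol 12.2.2):

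| Evaluable | Unconfirmed | Confirmed, period closed at EOCT |
|---|---|---|
| 3 | 1/3 = 33% (0.8 to 90.6) | 0/3 = 0% (0 to 70.8) |
| 5 | 1/5 = 20% (0.5 to 71.6) | 0/5 = 0% (0 to 52.2) |

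Across 15 evaluable subjects, assumed true response rates of 10%, 20% and 30% imply 1.5, 3.0 and 4.5 expected responders at EOCT. On scheduled scans all would be reported as none.

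**5. How an EOCT PR would be classed.** The nearest row of RECIST Table 3 is PR followed by not evaluable (NE), which gives "SD provided minimum criteria for SD duration met, otherwise NE". Since 70 days exceeds 56, SD is the most likely class and the disease control rate (DCR) is unchanged. The SAP does not say this. If such a subject were classed NE, DCR would fall.

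**6. If a post-EOCT scan may confirm.** Taking three months as 91 days, the next follow-up scan falls 77 to 105 days after EOCT. If additional cycles start at EOCT, the scan on Day 29 of the second one falls 28 + 28 = 56 days after EOCT. Protocol 4.2.1.2 doses the first three subjects of a cohort one week apart, so without delays their EOCT visits span 14 days. At a cut on the last subject's EOCT, the earliest subject in that cohort has 14 days of later follow-up, less than 56 or 77. The last-enrolled cohort therefore normally has no scheduled confirming scan by the cut.

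**7. Source of the rule.** The SAP cites RECIST. The attached guideline's comparison of versions 1.0 and 1.1 keeps confirmation only for non-randomised trials with response as the primary endpoint. The Phase I part is non-randomised, but response is not its primary endpoint.

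**The case against.** The softening phrase, as close to four weeks as possible, can be read as accepting the next available scan whenever it falls. RECIST 4.4.3 supports a longer view: "The best overall response is determined once all the data for the patient is known". SAP 3.2.18.1 also presents BOR again at two later points. This stands as a possible reading, but the visible SAP text does not adopt it, and step 6 shows that it does not help the last-enrolled cohort at this cut.

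Protocol 12.2.7 refers response-evaluation details to an image review charter that was not available, and part of the SAP appendices is redacted. Either might settle the point, so the criticism is limited to the visible text. A programmer working from SAP 3.2.18.1 would still need the rule there.

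Protocol 12.2.7 leaves analysis detail to the SAP, so adding confirmation may be delegated detail and not a protocol change. That is arguable. It could also be said that the study as a whole has ORR as a primary endpoint in Phase II, but this SAP covers only the Phase I dose escalation. The attribution to RECIST remains inaccurate for Phase I.

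Three stronger conclusions might be inferred, and the documents do not support them:
- *The core-trial ORR must be 0%.* Unscheduled scans are allowed, and the softening phrase may admit later ones.
- *Cohorts before the last are also unconfirmable at the cut.* That depends on enrolment pace, which the documents do not give.
- *Responses are lost, or the Phase II choice is misdirected.* SAP 3.2.18 lists every RECIST assessment by subject, and later cuts can include confirmation. Protocol 1.5 ties the Phase II design to the level of ORR but sets no threshold; Protocol 4.2.1.4 draws on accumulated subject data, and 4.3 requires an amendment.

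**Conclusion.** The point holds: SAP 3.2.18.1 is wrong as written for the core-trial cut. If the period closes at EOCT, scheduled scans give a confirmed ORR of 0/n at any true response rate, for example 0/3 instead of 1/3 or 0/5 instead of 1/5 with one EOCT PR. DCR is most likely unchanged. This assumes the nominal schedule and no unscheduled scan showing response at least 28 days before EOCT. Under the more generous reading, the last-enrolled cohort would still normally lack a scheduled confirming scan at a cut set at the last subject's EOCT.

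The practical weight is moderate. ORR here is secondary and descriptive, the intervals at three to five subjects overlap heavily, and escalation decisions rest on safety and organ exposure. The point should be fixed because this cut is both the SAP interim analysis and the main study report, and the misleading table is cheap to avoid.

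**What to change.** - At the core-trial cut, present BOR and ORR without the confirmation requirement, labelled unconfirmed.
- Present confirmed BOR and ORR only at cuts that include post-EOCT scans. State that such a scan may confirm an EOCT response, and how a CR or PR that stays unconfirmed is classed (SD or NE), because that choice can move DCR.
- Correct the attribution to RECIST. If confirmation is kept for Phase I, declare it in SAP section 5.

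The cost is SAP wording, one relabelled table and, if confirmation is kept, one section 5 entry. No scans or visits are added. The downside is that an unconfirmed ORR may include responses that later fail confirmation; the label is there to warn of this.

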### 3.2.18.2 Objective Response Rate

The proportion of subjects with a BOR characterised as either CR or PR according to RECIST criteria v1.1 relative to the total number of evaluable patients will be also presented by treatment group.

### 3.2.18.3 Disease Control Rate

The proportion of subjects with a BOR characterised as either CR, PR or SD according to RECIST criteria v1.1 relative to the total number of evaluable patients will be presented by treatment group.

### 3.2.18.4 Progression-Free Survival

The PFS according to local review will include investigator assessed PD and deaths. Other data will be censored. PFS will be assessed at the end of the core trial, at the end of the additional cycles and at the end of the long-term follow-up.

Definition of progression date:

The PD date is assigned to the first time at which PD can be declared.

Definition of censoring date:

Censoring dates are defined in subjects with no PD or death before end of period or withdrawal. In these subjects, the censoring date is defined as the last date on which progression status was 'adequately' assessed. This is taken to be the date of the last radiological assessment at which the target lesions were evaluated by local investigator review.

If no PD is documented, patient will be censored at the last available overall tumour assessment before start of the new anticancer therapy.

Definition of PFS time:

The PFS time will be calculated as the time from first treatment administration to either locally assessed PD or death.

$$\text{PFS time} = [(\text{Date of event} - \text{date of first treatment administration}) + 1] / 7 \text{ (weeks)}$$

The distribution of PFS times will be estimated using the Kaplan-Meier (KM) product limit method.

The Kaplan Meier method will provide hazard curves, life tables, median as well as corresponding 95% Confidence Interval (CI). These statistics will be presented for each treatment group.

### 3.2.18.5 Overall Survival

OS will be defined as the time from date of first treatment administration until death or last known alive. Any patient not known to have died at the time of analysis will be censored based at the last recorded date on which the patient was known to be alive (i.e. their status must be known at the censored date and should not be lost to follow up or unknown). OS will be assessed at the end of the core trial, at the end of the additional cycles and at the end of the long-term follow-up.

Definition of OS time:

The OS time will be calculated as the time from first treatment administration to death.

$$\text{OS time} = [(\text{Date of death or last date known to be alive} - \text{date of first treatment administration}) + 1] / 7 \text{ (weeks)}$$

OS will be analyzed using the same methodology (Kaplan-Meier) as described for the PFS.

### 3.2.18.6 *Metabolic tumour response*

Evaluation of metabolic tumour response using PERCIST will be summarised at each scheduled assessment by treatment group, for core trial and additional cycles separately. Corresponding information will be listed at each assessment by treatment group and subject, for core trial and additional cycles separately.

### 3.2.18.7 *Tumour markers in serum*

Tumour markers in serum will be listed at each assessment by treatment group and subject, for core trial and additional cycles separately.

The baseline will be defined as the last available (and reliable if applicable) assessment collected prior to first IMP administration.

Summary statistics by treatment group will be presented at each scheduled assessment for actual values and changes from baseline, for core trial and additional cycles separately.

